CLINICAL STUDY PROTOCOL

A Multicenter, Randomized, Parallel Group, Double Blind, Multiple Dose, Placebo Controlled Study to Assess the Efficacy and Safety of MNK-1411 in Male Subjects 4 to 8 Years of Age With Duchenne Muscular Dystrophy

NCT03400852

Summary adjusted for disclosure

Protocol Number: MNK14112096

Date of Original Protocol: 22 August 2017

Date of Protocol Amendment 1: 16 November 2017

Date of Protocol Amendment 2: 22 August 2018

Date of Protocol Amendment 3: 23 May 2019

Mallinckrodt ARD LLC
[name]
[name]
United States of America

PROTOCOL AMENDMENT 3

SUMMARY OF CHANGES

In order to accommodate subject needs, Protocol Amendment 3 was developed primarily to extend the Open Label Extension Period beyond Week 52 (to continue until the subject chooses to discontinue treatment, the investigator feels that treatment is no longer indicated, MNK-1411 is approved and marketed, or the sponsor ceases development of this compound for Duchenne Muscular Dystrophy [DMD]). Open label visits will continue every 12 weeks, with dispensing of study drug every 12 weeks. Along with this change, text has been added stating that if a subject requires a switch in dose during the Open Label Extension Period (eg, switch to low dose due to being unable to tolerate high dose, or switch to high dose based on increased weight [eg, as subject grows with age]), the investigator should consult with the medical monitor. Since subjects will be participating in the study longer, measurements of height have been added to all study visits.

Additional major protocol changes are summarized below and a more comprehensive [Summary of Changes](#) document, including minor protocol changes, is provided separately:

- To accommodate the needs of study sites in Israel, the combination of Sunday and Wednesday has been added as possible visit and/or dosage administration days.
- Text has been added specifying that subjects who have a hypersensitivity reaction to the study drug are not required to undergo the 2-week taper, or standard cosyntropin stimulation test (250 µg) at the follow-up visit.
- Varicella zoster testing has been added along with an inclusion criterion (Inclusion criterion 6) requiring subjects to test positive prior to study entry (since such infections may be serious in patients who are immunosuppressed).
- Pharmacokinetic analysis text has been corrected.
- Additional guidance regarding the administration of motor tests (10 Meter Walk/Run, Time to Climb 4 Standardized Stairs, Time to Stand from a Supine Position, North Starr Ambulatory Assessment [NSAA]) has been provided, along with modification of Exclusion criterion 7 to require that subjects be able to complete the 10 Meter Walk/Run test in 10 seconds or less at the Screening and Baseline Visits.

PROTOCOL AMENDMENT 2

SUMMARY OF CHANGES

Protocol Amendment 2 was developed to address the following considerations:

- In a randomized, double-blind, placebo controlled crossover study in patients ages 5 to 8 with Duchenne muscular dystrophy [Beenakker et al, 2005](#) utilized a 2 month washout period between treatment periods with prednisone and placebo and this washout period appeared to be effective. Subsequently a Medical Advisory Board evaluated the current study design and based on their clinical experience recommended allowing the enrollment of subjects who have not received a therapeutic dose of corticosteroids within 2 months prior to the start of the study.
- Subjects with asthma are excluded from the study. Therefore, the concomitant use of inhaled corticosteroids (whose approved indication is for asthma) should not be permitted.

The following changes were made:

Section 12.2, Exclusion criterion 2 was revised to:

2. Subject has had previous systemic treatment with corticosteroids within 2 months prior to the Screening Visit. Exception: In subjects who were down-titrated to a physiological dose of corticosteroids (ie, 3 mg/m² of prednisone or deflazacort) a maximum of 1 month of no greater than a physiological dose followed by 1 month completely off corticosteroids prior to the Screening Visit will be acceptable for study entry. Transient previous use of corticosteroids will be evaluated on a case-by-case basis by the sponsor or designee. The use of topical or intra-articular corticosteroids is permitted during the study.

Section 13.1, the exception for inhaled corticosteroids was deleted.

PROTOCOL AMENDMENT 1

SUMMARY OF CHANGES

Protocol Amendment 1 was developed to address issues raised by the central institutional review board including adding a study drug taper followed by a cosyntropin stimulation test and clarifying parent and/or legal guardian consent.

Additional minor changes that do not impact study conduct or subject safety were also made.

The major protocol changes are summarized below:

- A mandatory study drug taper has been added. All subjects will complete a 2-week taper after their last full dose of study drug. In the first week of the taper, each subject will receive one-half of their original dose administered 2 times per week for 1 week, followed by one-half of their original dose administered 1 time per week for 1 week.
- All subjects will have a standard cosyntropin stimulation test (250 µg) at their Follow-up Visit.
- References to “legally authorized representative” have been removed from the protocol. Only a parent or legal guardian can give consent for subjects to participate.
- The listing of chemistry laboratory tests in Attachment 1, [Section 32.1](#) has been clarified (creatinine updated to creatine phosphokinase).

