Entry Criteria: Male subjects 4 to 8 years of age (inclusive) with a diagnosis of DMD confirmed by complete dystrophin deficiency, an identifiable mutation of the DMD gene, or complete dystrophin gene sequencing consistent with DMD, and a clinical profile consistent with DMD. Subjects should have serum potassium within the reference range at screening. Subjects taking approved treatments that target gene mutation (eg, eteplirsen or ataluren) may be enrolled in the study if they have been on a stable dose for 30 days prior to the first dose of study drug, and plan to remain on that dose throughout the study. Subjects will be excluded if they have symptomatic cardiomyopathy; have had any previous systemic treatment with corticosteroids within 2 months prior to the Screening Visit; or treatment with immunosuppressants or mineralocorticoids in the 3 months prior to the Screening Visit. Subjects must be able to complete the 10 Meter Walk/Run test in 10 seconds or less at the Screening and Baseline Visits.	

Study Title: A Multicenter, Randomized, Parallel Group, Double Blind, Multiple Dose, Placebo Controlled Study to Assess the Efficacy and Safety of MNK-1411 in Male Subjects 4 to 8 Years of Age With Duchenne Muscular Dystrophy	
Protocol Number: MNK14112096	Type: Phase 2
Condition/Disease:	Duchenne Muscular Dystrophy
Concomitant Medications and Treatments: Subjects are not permitted to receive live or live-attenuated vaccines (with the exception of the varicella zoster vaccine, if needed per Inclusion criterion 6), systemic corticosteroids (eg, prednisone or deflazacort) for DMD, mineralocorticoids, or immunosuppressants during the study. All medications and nondrug therapies (eg, physical therapy, blood transfusions, oxygen supplementation, etc) taken from 30 days prior to the Screening Visit and throughout the study will be recorded.	
Study Drug and Treatment Administration:	
The following treatments will be administered during the 24 week Blinded Treatment Period:	

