The pharmacokinetics (PK) of MNK-1411 in DMD patients will be characterized using population PK modeling with sparse PK sampling implemented in this study. The exposure response (selected efficacy and/or safety endpoints at Week 4) relationship will be explored.	
Safety Evaluations:	
The following safety assessments will be evaluated: adverse events, medical history, physical examinations, concurrent medical conditions, height, weight, clinical laboratory tests, vital signs, electrocardiograms, and antidrug antibodies.	

Study Title: A Multicenter, Randomized, Parallel Group, Double Blind, Multiple Dose, Placebo Controlled Study to Assess the Efficacy and Safety of MNK-1411 in Male Subjects 4 to 8 Years of Age With Duchenne Muscular Dystrophy

Protocol Number: MNK14112096	Type: Phase 2
Condition/Disease:	Duchenne Muscular Dystrophy

Quality of Life/ Health Outcome Evaluations:

The following quality of life /health outcome assessment will be evaluated: Pediatric Outcomes Data Collection Instrument (PODCI).

Statistical Methods:

Analysis Populations

The following analysis populations are defined for this study:

- The Modified Intent-to-Treat (mITT) Population will include all randomized subjects who receive 1 or more doses of study drug and who contribute any efficacy data to the study.
- The Safety Population will include all subjects who receive 1 or more doses of study drug.
- The PK Population will include all subjects who provide at least 1 quantifiable concentration of ACTH₁₋₂₄ following the administration of at least 1 complete dose of study drug, and without any major protocol deviations that compromise the PK samples.

Sample Size

A total of 132 subjects will be randomized in this study (44 per treatment group). The sample size was determined using the change from baseline in the 10 Meter Walk/Run time. With 37 subjects per treatment group expected to complete the Blinded Treatment Period, the trial will have an 80% power to detect a 1 second treatment difference comparing 2 groups at a significance level of 0.05. Taking into account a dropout rate of approximately 15%, the sample size for this study will be 44 subjects per treatment arm.

Efficacy Analysis

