Unless otherwise specified, all statistical tests will be two-sided with a significance level of 0.05. Summary statistics will be provided for all study variables with descriptive statistics (number of observations, mean, SD, median, minimum, and maximum) for numerical (or continuous) variables, and frequency and percentages will be calculated for categorical variables. All data will be summarized by treatment groups as appropriate. The 2 placebo groups will be combined for all analyses. Data summary and analyses will be performed with SAS 9.4 or higher.

The primary efficacy endpoint is a change from baseline in 10 Meter Walk/Run time at Week 24. The primary statistical analysis method for the endpoint will be performed using an analysis of variance (ANOVA) model with treatment as a main factor and baseline value as a covariate.

The secondary efficacy endpoints will be analyzed using the same statistical method as that for the primary efficacy endpoint.

Additional exploratory analyses [REDACTED]
[REDACTED]

Pharmacokinetic Analysis

Population PK analysis for MNK-1411 will be conducted using nonlinear mixed effects modeling.

Safety Analysis

Treatment-emergent adverse events and serious adverse events will be summarized using the appropriate version of MedDRA by preferred term within system organ class. Other safety data will be listed and summarized descriptively or graphically, as appropriate.

Study Title: A Multicenter, Randomized, Parallel Group, Double Blind, Multiple Dose, Placebo Controlled Study to Assess the Efficacy and Safety of MNK-1411 in Male Subjects 4 to 8 Years of Age With Duchenne Muscular Dystrophy

Protocol Number: MNK14112096	Type: Phase 2
Condition/Disease:	Duchenne Muscular Dystrophy

Quality of Life/Health Outcomes Analysis

The PODCI (sport and physical functioning domain and transfer/basic mobility domain) will be summarized at baseline and each study visit. Change from baseline to Weeks 4, 8, 12, 16, and 24 in PODCI domains also will be summarized. The change from baseline data will be analyzed using the same methods as those used for the primary efficacy endpoint.

Open Label Extension Analysis

In the Open Label Extension Period, efficacy data will be summarized at each visit. Safety data will also be summarized as appropriate.

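### Prior corticosteroid use may vary widely among enrolled boys, but the stated primary model leaves it out; adding it is a cheap gain in precision and interpretability, not a repair of bias

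*Combined protocol and SAP*

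**What the plan says.** The Amendment 2 summary of changes says that a medical advisory board "recommended allowing the enrollment of subjects who have not received a therapeutic dose of corticosteroids within 2 months prior to the start of the study". The reasons given are a crossover study in which a 2-month washout appeared effective, and clinical experience. This is not superseded text: the Entry Criteria in the current synopsis (Section 6) exclude boys who "have had any previous systemic treatment with corticosteroids within 2 months prior to the Screening Visit". As set out in the Amendment 2 summary, Exclusion criterion 2 adds an exception. After down-titration, up to 1 month at a physiological dose followed by 1 month completely off is acceptable. Transient earlier use is judged case by case.

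The synopsis gives 2:2:1:1 allocation and names no stratification factor. The primary endpoint, change in 10 Meter Walk/Run time at Week 24, is analysed by an "analysis of variance (ANOVA) model with treatment as a main factor and baseline value as a covariate", and the secondary endpoints use the same method. On size: "The sample size was determined using the change from baseline in the 10 Meter Walk/Run time", and "the trial will have an 80% power to detect a 1 second treatment difference comparing 2 groups at a significance level of 0.05".

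**The concern.** The entry rule allows a spread of corticosteroid histories: never treated, stopped long ago, stopped about 2 months before Screening, or only 1 month fully off. The stated support for the washout does not say that motor function is stable over the following 24 weeks, which is when the primary endpoint accrues. The baseline covariate captures function already lost by Baseline. It does not capture a decline that continues afterwards.

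If history predicts the 24-week change, two things follow. Variance that a prespecified covariate could remove stays in the error term. The single overall estimate also leaves open whether MNK-1411 works in boys who never had corticosteroids, a question any reader of a positive result will ask. An adjustment or split introduced after unblinding would be post hoc.

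**Working it through.** **Inputs from the synopsis.** Testing: "all statistical tests will be two-sided with a significance level of 0.05". Target difference 1 s, power 80%. Completers: "With 37 subjects per treatment group expected to complete the Blinded Treatment Period". Inflation: "Taking into account a dropout rate of approximately 15%, the sample size for this study will be 44 subjects per treatment arm".

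**Inputs not given, so assumed.** Share of previously treated boys f = 10% to 50%. Difference in 24-week change between histories d = 0.5 to 1.5 s. The SD of change is not stated either and is back-solved below.

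**1. The plan's own figures.** 37 / 0.85 = 43.5, rounded up to 44; 3 × 44 = 132. Both reproduce. For a two-sample t test with 37 per group, 72 degrees of freedom and noncentrality 1 / (SD × √(2/37)), power of 80% requires SD = 1.515 s (variance 2.294 s²). The normal approximation gives 1.54 s.

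**2. Adjustment when the difference d occurs in both arms.** Variance explained by history is f(1 − f)d². For f = 0.3 and d = 1.0 this is 0.21 s², or 9.2% of 2.294. The adjusted SD is √(2.294 − 0.21) = 1.444 s. Power for 1 s (noncentral t, 37 per group, ignoring the one degree of freedom) is:

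| Share f | d = 0.5 s | d = 1.0 s | d = 1.5 s |
|---|---|---|---|
| 10% | 80.4% | 81.5% | 83.5% |
| 20% | 80.7% | 82.8% | 86.2% |
| 30% | 80.9% | 83.6% | 88.2% |
| 50% | 81.1% | 84.3% | 89.7% |

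**3. Adjustment when d occurs on placebo only and is fully reversed on drug.** A common term for history then removes only f(1 − f)d²/4 of the average variance. For f = 0.3, power is 80.2%, 80.9% and 82.0% at d = 0.5, 1.0 and 1.5 s. For f = 50% and d = 1.5 s it is 82.4%, the highest value in the range.

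**4. Chance imbalance.** The 95% range of the shift in a dose-placebo difference is 1.96 × d × √(2f(1 − f)/37). For f = 0.3 this is ±0.21 s at d = 1.0 and ±0.31 s at d = 1.5. It is already part of the sampling error, whose half-width is 1.96 × 1.515 × √(2/37) = 0.69 s. Removing it leaves √(0.69² − 0.21²) = 0.66 s, or √(0.69² − 0.31²) = 0.62 s.

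**5. What an estimate by history can show.** With f = 0.3, the 95% half-width is 1.96 × 1.515 × √(2/25.9) = 0.82 s in never-treated boys (0.7 × 37 = 25.9 per group) and 1.96 × 1.515 × √(2/11.1) = 1.26 s in previously treated boys (0.3 × 37 = 11.1 per group). The standard error of a treatment-by-history interaction is 1.515 × √(2/(37f) + 2/(37(1 − f))), which is 0.88, 0.77 and 0.70 s at f = 20%, 30% and 50%. Power for a 1 s interaction is then about 20% to 29%.

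**The case against.** A reader might infer that the trial certainly does not stratify, and that its primary effect therefore blends new benefit with reversal of withdrawal decline. The documents do not support that.

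- **The absence is not proven.** Only amendment summaries and a synopsis are available, and part of the exploratory analysis text is redacted. Silence in a synopsis shows only that no stratification is described. The terms of the primary model, by contrast, are explicit.
- **There is no bias.** Randomisation against concurrent placebo estimates the effect for the enrolled mix without bias, and omitting the covariate does not invalidate the test. The primary objective concerns boys with DMD, not never-treated boys in particular.
- **The mechanism is unproven.** No passage shows that course or effect differs by history. The plan reports that a 2-month washout appeared effective. Two months is the minimum under the general rule, screening can add up to 28 days, and Baseline follows that. The rule also admits boys who stopped long before.
- **Large gains need large inputs.** Power of 84% to 88% requires, at a 30% share, a shift of 1.0 to 1.5 s in both arms, which is as large as the whole target effect or larger. It also conflicts with a story in which the decline occurs on placebo and is reversed on drug.
- **A main effect still gives one averaged result**, and an interaction test would be weak.

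All of this stands, and it limits both the claim and its size. It does not identify a material downside to prespecifying the covariate or to a supportive estimate by history.

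**Conclusion.** The point holds as a cheap improvement. The entry rule permits mixed corticosteroid histories, the stated primary model omits them, and nothing in the supplied text analyses by them. The primary test is not in error and the sample size stands.

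Under the assumed ranges, adjustment takes power for 1 s from 80% to about 80% to 84% if histories differ by up to 1.0 s in both arms. It reaches at most about 90%, at 1.5 s with a 50% share. If the difference arises on placebo alone, the figure is about 80% to 82%. All of these rest on an SD back-solved from the stated power and on shares and differences that the documents do not give. The gain in interpretability is descriptive: an estimate in never-treated boys with a half-width of about 0.8 s at a 30% share.

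**What to change.** - At Screening, record whether the boy ever had systemic corticosteroids for DMD and, if so, the date of the last dose.
- Before unblinding, prespecify prior use (never / previously treated) as a covariate in the primary model, with time since last dose if numbers allow, since recency is the likelier driver.
- Report the dose-placebo difference with its interval by prior use, labelled descriptive and supportive.
- Optionally, add prior use as an IXRS stratum for boys still to be randomised.
- If the full protocol or SAP already contains any of this, state it in the synopsis.

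Cost: one data field, one degree of freedom and one table with wide subgroup intervals. No extra patients or procedures are needed, and the entry criteria do not change.

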5. ABBREVIATIONS

Abbreviation	Term
2x/week	2 times per week
ACTH	Adrenocorticotropic hormone
AE	Adverse event
ANOVA	Analysis of variance
AUC	Area under the concentration time curve
CFR	Code of Federal Regulations
CL	Clearance
CL/F	Apparent clearance
C _{max}	Peak drug concentration
eCRF	Electronic case report form
DMD	Duchenne muscular dystrophy
ECG	Electrocardiogram
FDA	Food and Drug Administration
FVC	Forced vital capacity
HbA1c	Glycosylated hemoglobin
HBsAg	Hepatitis B surface antigen
HBcAb	Hepatitis B core antibody
HCV	Hepatitis C virus antibody
HIPAA	Health Insurance Portability and Accountability Act
ICF	Informed consent form
ICH	International Council for Harmonisation
ID	Identification
IEC	Independent Ethics Committee
IGRA	Interferon gamma release assay
IM	Intramuscular, intramuscularly
IMP	Investigational medicinal product
IRB	Institutional Review Board
IXRS	Interactive Phone/Web Response System
MCR	Melanocortin receptor
mITT	Modified Intent-to-Treat
MM	Medical monitor
NSAA	North Star Ambulatory Assessment
PCR	Polymerase chain reaction
PD	Pharmacodynamics

Abbreviation	Term
PK	Pharmacokinetics
PODCI	Pediatric Outcomes Data Collection Instrument
SAE	Serious adverse event
SC	Subcutaneous, subcutaneously
TB	Tuberculosis
TEAE	Treatment-emergent adverse event
TFT	Timed function tests
US	United States
V	Volume of distribution
WT _{DMD}	Weight in kg of the DMD subject

6. SYNOPSIS

Study Title: A Multicenter, Randomized, Parallel Group, Double Blind, Multiple Dose, Placebo Controlled Study to Assess the Efficacy and Safety of MNK-1411 in Male Subjects 4 to 8 Years of Age With Duchenne Muscular Dystrophy	
Protocol Number: MNK14112096	Type: Phase 2
Condition/Disease:	Duchenne Muscular Dystrophy
Approximate Number of Subjects: 132	Approximate Duration of Subject Participation: 24 weeks for the Blinded Treatment Period, Open Label Extension Period until study termination.
Approximate Number of Study Centers: 50 globally	Approximate Duration of Study: The Blinded Treatment Period portion of the study is estimated to be 3 years.
Design: This is a multicenter, double blind, placebo controlled, multiple dose study to examine the safety and efficacy of MNK-1411 in male subjects 4 to 8 years of age (inclusive) with Duchenne Muscular Dystrophy (DMD). Approximately 150 subjects will be screened in order to randomize 132 (44 per treatment group). Following a screening period of up to 28 days, subjects will be randomized on a 2:2:1:1 basis to receive 24 weeks of treatment with 2 weight based doses of MNK-1411 or volume matched placebo administered 2x/week. Subjects will return to the clinic for visits at 4, 8, 12, 16, and 24 weeks after their first dose of study drug. Subjects who complete the 24-week Blinded Treatment Period will be eligible to enter an Open Label Extension Period where all subjects will receive treatment with MNK-1411. Participation in the Open Label Extension Period will continue until the subject chooses to discontinue treatment, the investigator feels that treatment is no longer indicated, MNK-1411 is approved and marketed, or the sponsor ceases development of this compound for DMD. All subjects will complete a 2-week drug taper after their last full dose of study drug and a follow-up visit 28 (\pm 7) days after their last full dose of study drug. The taper is not required for any subject who has a hypersensitivity reaction to the study drug.	
Objectives: Primary Objective To determine the effect of MNK-1411 on motor function in subjects with DMD. Secondary Objectives To assess the effect of MNK-1411 on motor skills and strength. To determine the safety and tolerability of MNK-1411 in subjects with DMD. Exploratory Objectives 	
Entry Criteria: Male subjects 4 to 8 years of age (inclusive) with a diagnosis of DMD confirmed by complete dystrophin deficiency, an identifiable mutation of the DMD gene, or complete dystrophin gene sequencing consistent with DMD, and a clinical profile consistent with DMD. Subjects should have serum potassium within the reference range at screening. Subjects taking approved treatments that target gene mutation (eg, eteplirsen or ataluren) may be enrolled in the study if they have been on a stable dose for 30 days prior to the first dose of study drug, and plan to remain on that dose throughout the study. Subjects will be excluded if they have symptomatic cardiomyopathy; have had any previous systemic treatment with corticosteroids within 2 months prior to the Screening Visit; or treatment with immunosuppressants or mineralocorticoids in the 3 months prior to the Screening Visit. Subjects must be able to complete the 10 Meter Walk/Run test in 10 seconds or less at the Screening and Baseline Visits.	

Study Title: A Multicenter, Randomized, Parallel Group, Double Blind, Multiple Dose, Placebo Controlled Study to Assess the Efficacy and Safety of MNK-1411 in Male Subjects 4 to 8 Years of Age With Duchenne Muscular Dystrophy	
Protocol Number: MNK14112096	Type: Phase 2
Condition/Disease:	Duchenne Muscular Dystrophy
Concomitant Medications and Treatments: Subjects are not permitted to receive live or live-attenuated vaccines (with the exception of the varicella zoster vaccine, if needed per Inclusion criterion 6), systemic corticosteroids (eg, prednisone or deflazacort) for DMD, mineralocorticoids, or immunosuppressants during the study. All medications and nondrug therapies (eg, physical therapy, blood transfusions, oxygen supplementation, etc) taken from 30 days prior to the Screening Visit and throughout the study will be recorded.	
Study Drug and Treatment Administration:	
The following treatments will be administered during the 24 week Blinded Treatment Period:	

• Treatment A: MNK-1411 0.5 mg (0.5 mL, for subjects weighing more than 20 kg) or 0.4 mg (0.4 mL, for subjects weighing less than or equal to 20 kg) administered SC 2 times per week (2x/week) (administered on either Sunday and Wednesday, Monday and Thursday, Tuesday and Friday, or Wednesday and Saturday).• Treatment B: MNK-1411 0.25 mg (0.25 mL, for subjects weighing more than 20 kg) or 0.2 mg (0.2 mL, for subjects weighing less than or equal to 20 kg) administered SC 2x/week (administered on either Sunday and Wednesday, Monday and Thursday, Tuesday and Friday, or Wednesday and Saturday).• Treatment C: Volume matched placebo (0.5 mL for subjects weighing more than 20 kg or 0.4 mL for subjects weighing less than or equal to 20 kg) administered SC 2x/week (administered on either Sunday and Wednesday, Monday and Thursday, Tuesday and Friday, or Wednesday and Saturday).• Treatment D: Volume matched placebo (0.25 mL for subjects weighing more than 20 kg or 0.2 mL for subjects weighing less than or equal to 20 kg) administered SC 2x/week (administered on either Sunday and Wednesday, Monday and Thursday, Tuesday and Friday, or Wednesday and Saturday).	
During the Open Label Extension Period, subjects will be treated with MNK-1411 at the dose administered during the Blinded Treatment Period. If a subject requires a switch in dose (eg, switch to low dose due to being unable to tolerate high dose, or switch to high dose based on increased weight [eg, as subject grows with age]), the investigator should consult with the medical monitor. No switches in dose are permitted during the Blinded Treatment Period.	
All subjects will complete a 2-week taper after their last full dose of study drug. In the first week of the taper, each subject will receive one-half of their original dose administered 2x/week for 1 week, followed by one-half of their original dose administered 1 time per week for 1 week. The taper is not required for any subject who has a hypersensitivity reaction to the study drug.	
Efficacy Evaluations:	
The following efficacy assessments will be evaluated: 10 Meter Walk/Run, North Star Ambulatory Assessment (NSAA), Time to Climb 4 Standardized Stairs, Time to Stand from A Supine Position, quantitative muscle testing, pulmonary function tests, and biomarkers.	
Pharmacokinetic and Pharmacodynamic Evaluations:	
The pharmacokinetics (PK) of MNK-1411 in DMD patients will be characterized using population PK modeling with sparse PK sampling implemented in this study. The exposure response (selected efficacy and/or safety endpoints at Week 4) relationship will be explored.	
Safety Evaluations:	
The following safety assessments will be evaluated: adverse events, medical history, physical examinations, concurrent medical conditions, height, weight, clinical laboratory tests, vital signs, electrocardiograms, and antidrug antibodies.	

Study Title: A Multicenter, Randomized, Parallel Group, Double Blind, Multiple Dose, Placebo Controlled Study to Assess the Efficacy and Safety of MNK-1411 in Male Subjects 4 to 8 Years of Age With Duchenne Muscular Dystrophy

Protocol Number: MNK14112096	Type: Phase 2
Condition/Disease:	Duchenne Muscular Dystrophy

Quality of Life/ Health Outcome Evaluations:

The following quality of life /health outcome assessment will be evaluated: Pediatric Outcomes Data Collection Instrument (PODCI).

Statistical Methods:

Analysis Populations

The following analysis populations are defined for this study:

- The Modified Intent-to-Treat (mITT) Population will include all randomized subjects who receive 1 or more doses of study drug and who contribute any efficacy data to the study.
- The Safety Population will include all subjects who receive 1 or more doses of study drug.
- The PK Population will include all subjects who provide at least 1 quantifiable concentration of ACTH₁₋₂₄ following the administration of at least 1 complete dose of study drug, and without any major protocol deviations that compromise the PK samples.

Sample Size

A total of 132 subjects will be randomized in this study (44 per treatment group). The sample size was determined using the change from baseline in the 10 Meter Walk/Run time. With 37 subjects per treatment group expected to complete the Blinded Treatment Period, the trial will have an 80% power to detect a 1 second treatment difference comparing 2 groups at a significance level of 0.05. Taking into account a dropout rate of approximately 15%, the sample size for this study will be 44 subjects per treatment arm.

Efficacy Analysis

Unless otherwise specified, all statistical tests will be two-sided with a significance level of 0.05. Summary statistics will be provided for all study variables with descriptive statistics (number of observations, mean, SD, median, minimum, and maximum) for numerical (or continuous) variables, and frequency and percentages will be calculated for categorical variables. All data will be summarized by treatment groups as appropriate. The 2 placebo groups will be combined for all analyses. Data summary and analyses will be performed with SAS 9.4 or higher.

The primary efficacy endpoint is a change from baseline in 10 Meter Walk/Run time at Week 24. The primary statistical analysis method for the endpoint will be performed using an analysis of variance (ANOVA) model with treatment as a main factor and baseline value as a covariate.

The secondary efficacy endpoints will be analyzed using the same statistical method as that for the primary efficacy endpoint.

Additional exploratory analyses [REDACTED]
[REDACTED]

Pharmacokinetic Analysis

Population PK analysis for MNK-1411 will be conducted using nonlinear mixed effects modeling.

Safety Analysis

Treatment-emergent adverse events and serious adverse events will be summarized using the appropriate version of MedDRA by preferred term within system organ class. Other safety data will be listed and summarized descriptively or graphically, as appropriate.

Study Title: A Multicenter, Randomized, Parallel Group, Double Blind, Multiple Dose, Placebo Controlled Study to Assess the Efficacy and Safety of MNK-1411 in Male Subjects 4 to 8 Years of Age With Duchenne Muscular Dystrophy

Protocol Number: MNK14112096	Type: Phase 2
Condition/Disease:	Duchenne Muscular Dystrophy

Quality of Life/Health Outcomes Analysis

The PODCI (sport and physical functioning domain and transfer/basic mobility domain) will be summarized at baseline and each study visit. Change from baseline to Weeks 4, 8, 12, 16, and 24 in PODCI domains also will be summarized. The change from baseline data will be analyzed using the same methods as those used for the primary efficacy endpoint.

Open Label Extension Analysis

In the Open Label Extension Period, efficacy data will be summarized at each visit. Safety data will also be summarized as appropriate.
